### 3.3 Analysis sets

For all analysis sets, participants will be analyzed according to the study treatment(s) initially received.

The safety analysis set will include all participants that received any study drug (including the participants who received the 75 mg).

The PK analysis set will include all participants with at least one available valid (i.e. not flagged for exclusion) PK concentration measurement, who received any study drug and with no protocol deviations that impact on PK data.

The PD analysis set will include all participants with available PD data and no protocol deviations with relevant impact on PD data.

The analysis sets and protocol deviation codes are related as follows:

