9.1.6 Treatment arm stopping rules

Any of the treatment arms will be paused with no further dosing of that dose level pending a full safety review, if any of the following criteria are met:

- Two (2) or more subjects in the same treatment arm present with moderate or severe injection site AE of warmth and swelling that is deemed as possibly or probably related to LRX712 injection.
- The Sponsor considers that the number and/or severity of AEs, abnormal safety monitoring tests or abnormal laboratory findings justify putting the treatment arm on hold.

In the event that one treatment arm is paused for full safety review, the other treatment arm and the placebo arm will continue as per assessment schedule.

If after the full safety review of the paused treatment arm the Sponsor considers that it needs to be stopped, the study will continue with the placebo arm and the other treatment arm e.g., placebo and 15 mg LRX712.

The study subjects randomized to the stopped treatment arm may continue the study or resume dosing following the safety review, if the Investigator and Sponsor agree it is safe to proceed for them e.g. they did not experienced any of the injection site AEs that led to the discontinuation of study treatment and pausing that treatment arm:

1. In the event any subject has not completed the full dosing regimen (3 doses), he/she will continue the study on the other dose level until completing the full dosing regimen e.g., 15 mg LRX712
2. In the event any subject has completed the full dosing regimen, he/she will continue the study per the assessment schedule

The pending number of subjects that would have been randomized to the stopped treatment arm will be randomized to the other treatment arm e.g., if the 25 mg LRX712 treatment arm was stopped after 5 subjects were randomized to it, then the remaining 10 will be randomized to the 15 mg LRX712 by means of a new randomization list.

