12.1 Analysis sets

For all analysis sets, subjects will be analyzed according to the study treatment(s) received.

The safety analysis set will include all subjects that received any study drug.

The PK analysis set will include all subjects with at least one available valid (i.e., not flagged for exclusion) PK concentration measurement, who received any study drug and with no protocol deviations that impact on PK data.

The PD analysis set will include all subjects with available PD data and no protocol deviations with relevant impact on PD data.

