## 1.4 Primary estimand(s)

The primary clinical question of interest is: What is the effect of LRX712 treatment versus placebo on change from baseline at Week 28 in the medial femoral condyle cartilage volume in the index region in patients with mild/moderate knee OA?

The justification for the primary estimand is that it will capture the effect of the study drug under the research conditions versus placebo within the context of the protocol-specified guidelines for use of additional basic pain medication, and the use of rescue medications.

The primary estimand is described by the following attributes:

1. Population: participants suffering from symptomatic knee OA. Further details about the population are provided in [Section 5 - Protocol](#).
2. Endpoint: efficacy is to be measured using the change from baseline to Week 28 of the double-blind study period in the medial femoral condyle cartilage volume in the index region.
3. Treatment of interest: the randomized treatments (the investigational treatment LRX712 or the control treatment) plus, if needed, intake of the allowed basic pain medication and the use of rescue medication. Further details about the investigational treatment and control treatment are provided in [Section 6 - Protocol](#).
4. Identification of possible Intercurrent Events (ICEs):
  - At least one dose administration missed.These ICEs will be handled according to a hypothetical strategy, as if the ICE had not occurred (see Section 4.1.3 for details).
5. Summary measure: the difference between treatments in the mean changes from baseline to Week 28 of the double-blind study period in the medial femoral condyle cartilage volume in the index region .

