## **4 Statistical methods for Pharmacodynamic (PD) parameters**

All participants within the primary PD analysis set will be included in the PD data analysis, unless otherwise stated.

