#### **4.1.3 Handling of intercurrent events**

All ICEs listed in Section 1.4 will be handled by a hypothetical strategy to estimate what the treatment effect would have been at Week 28 if all participants adhered to the initially randomized treatment through that time point. In the case of ICEs such as missing at least one dose administration the assessments collected post-ICE occurrence will not be evaluated for the purposes of the primary estimand. Although data post-ICEs are not required for the primary estimand, these assessments will be collected for estimation of secondary and/or supportive estimands.

Assessments collected post-ICE will be considered missing and implicitly imputed by the MMRM under the MAR assumption (i.e. assuming that participants with missing data would have efficacy outcomes like those of similar participants in their treatment who continue their randomized treatment). In case of an unexpectedly high number of discontinuations (in particular due to a similar reason) from the investigational treatment are observed, the assumptions underlying the strategy considered might be revised and modified as appropriate.

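### The primary estimand is defined by randomised treatment, but every analysis set groups by treatment received, and neither a wrong treatment nor a dose-level switch is an intercurrent event

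*SAP*

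**What the plan says.** **Grouping.** SAP 3.3: "For all analysis sets, participants will be analyzed according to the study treatment(s) initially received". Protocol 12.1: "For all analysis sets, subjects will be analyzed according to the study treatment(s) received". The protocol sentence lacks the restriction to the first treatment.

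**Set used for the primary analysis.** SAP 3.3 defines the efficacy set without reference to randomisation: "The PD analysis set will include all participants with available PD data and no protocol deviations with relevant impact on PD data". SAP section 4 then applies it: "All participants within the primary PD analysis set will be included in the PD data analysis, unless otherwise stated". Neither document defines a set grouped as randomised, and neither exempts the PD set from the as-received rule.

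**Estimand.** SAP 1.4, item 3, begins: "Treatment of interest: the randomized treatments (the investigational treatment LRX712 or the control treatment", and then adds permitted pain and rescue medication. SAP 4.1.3 targets the Week 28 effect "if all participants adhered to the initially randomized treatment through that time point". The single intercurrent event in SAP 1.4, item 4, is: "At least one dose administration missed".

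**Dose-level switch.** Under Protocol 9.1.6, if an arm is stopped, a participant from that arm who has had fewer than three doses and is judged safe to proceed is handled as follows: "he/she will continue the study on the other dose level until completing the full dosing regimen".

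**Deviations.** SAP Table 3-1 lists one deviation that removes a participant from the PD set, failure to obtain written consent first. Additions require a SAP amendment before database lock.

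**The concern.** The estimand and the grouping rule rest on different bases. They coincide as long as everyone receives the randomised treatment throughout. When someone does not, the plan gives no answer that follows from its own estimand. A participant given another arm's treatment at the first injection would be analysed in that other arm. A participant moved to the other dose level part-way would count in full in the first arm under the SAP, although the estimand asks what would have happened had that person stayed on the randomised dose. Under the protocol's wording, that participant's group cannot be determined.

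What is at stake is pre-specification. If such a case arises, someone must choose between two written rules. Protocol 6.4 gives the study statistician and programmers access to treatment assignments from the start, so the choice could be made with the allocation known.

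**Working it through.** **1. The plan's own figure.** Inputs from SAP section 7 and Protocol 12.8.1: difference 123 mm³, SD 130 mm³, 13 per arm, two-sided 10% level.

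- Standard error = 130 × √(2/13) = 50.99 mm³; 123 / 50.99 = 2.412.
- Normal approximation: Φ(2.412 − 1.645) = 77.9%, which matches the SAP's 78%.
- Noncentral t with 24 df: 75.8%, consistent with the protocol's approximately 75%.

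The grouping rule does not enter this calculation, so no planned figure changes.

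**2. What the rules do, case by case.**

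| Situation | Group under SAP 3.3 | Group under Protocol 12.1 | Intercurrent event? | In line with the estimand? |
|---|---|---|---|---|
| All doses as randomised | Randomised arm | Randomised arm | No | Yes |
| Wrong treatment at dose 1, detected | Arm received | Arm received at dose 1; unclear if later doses differ | No | No |
| Wrong treatment at dose 2 or 3 only, detected | Randomised arm, all data used | Not determined | No | No |
| Switch to the other dose level (Protocol 9.1.6) | First arm, all data used | Not determined | No | No |
| Wrong treatment, never detected | Recorded as assigned | Recorded as assigned | Cannot be applied | No rule can act |

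A pause of an arm could also cause a scheduled injection to be missed, and the existing intercurrent event would then apply. Protocol 9.1.6, however, describes completing all three doses at the other level, and that is not a missed dose.

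**3. Size.** The documents give no error rate, so any count is an assumption. One participant is 1/13 = 7.7% of an arm. As an illustration, assume one participant randomised to active drug receives placebo and responds to what was received (t-test, two-sided 10%):

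- As received: 12 vs 14, standard error 130 × √(1/12 + 1/14) = 51.14 mm³, expected contrast 123 mm³, power 75.5%.
- As randomised, with the data kept: 13 vs 13, expected contrast 123 × (1 − 1/13) = 113.5 mm³, power 69.8%.

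With two such participants the figures are 123 mm³ and 74.9% (11 vs 15) against 104.1 mm³ and 63.3%.

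**4. Consequence of making it an intercurrent event.** Injections are on Days 1, 29 and 57 (Protocol 6.1.3). MRI is at Screening and Weeks 16, 28 and 52 (Protocol 3.2). Every injection therefore precedes the first post-baseline scan. SAP 4.1.3 treats assessments after the event as missing, and SAP 4.1.4 requires at least one post-randomisation measurement. A participant affected at any injection thus leaves the primary model. One loss gives 12 vs 13 and a standard error of 130 × √(1/12 + 1/13) = 52.04 mm³, which is 52.04 / 50.99 = 1.02 times the planned value (a two-sample approximation without the repeated measures). A missed dose already has this consequence under the present text.

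**The case against.** **The PD set can already exclude a mis-dosed participant.** A reader might infer that nothing in the plan would catch a wrong treatment. That is too strong. The PD set excludes deviations with relevant impact on PD data, treatment errors are recorded on the dosing eCRF (Protocol 10.1.5), and Table 3-1 can be amended before lock. It remains true that this exclusion is available but not pre-coded.

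**The dilution figure does not measure harm from the current rule.** A reader might compute 123/13 = 9.5 mm³ per mis-dosed participant and call it bias. That loss arises when the participant is kept in the randomised arm, which SAP 3.3 does not do. In the illustration, as-received grouping retains 123 mm³ and almost all the power. The documents support no estimate of bias from the present rule.

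**Frequent errors cannot be inferred.** Allocation without IRT and site dilution from open-label bulk may suggest that errors are likely. Against that, unblinded monitors check allocation, a second unblinded person injects, white suspension and clear saline differ visibly, and plasma from active arms is assayed (Protocol 6.1.1, 6.4, 8.5.1.1). Placebo samples are not assayed, but an undetected error cannot move anyone between groups. A mix-up between 15 mg and 25 mg would be harder to see.

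**The rule has a rationale.** The SAP's restriction to the first treatment keeps switched participants in one definite group, and the study is declared exploratory. Both points are fair, and they lower the severity. They do not reconcile SAP 3.3 with SAP 1.4, and they leave Protocol 12.1 different from the SAP.

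**Conclusion.** The inconsistency is real and minor. The written grouping rule and the single intercurrent event do not deliver the stated estimand after a detected wrong-treatment administration or after a dose-level switch under Protocol 9.1.6. The effect on the result is zero if neither occurs. If one does, it concerns 7.7% of a 13-subject arm per participant. The power figures above rest on an assumed number of errors and on participants responding to what they received.

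A reader might go further and conclude that the planned efficacy comparison is not one of randomised groups. The documents do not support that as a general statement: under the SAP, grouping departs from randomisation only when the first treatment given is known to differ from the one assigned.

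**What to change.** 1. **SAP 3.3:** analyse the PD set by randomised treatment; keep treatment received for the safety and PK sets.
2. **SAP 1.4, item 4:** add *received a treatment or dose level other than the randomised one* as an intercurrent event, under the existing hypothetical strategy.
3. **Protocol 12.1:** align it with the amended SAP text, so that the two documents no longer differ on first versus any treatment received.
4. **Supportive analysis:** repeat the primary model with affected participants kept in their randomised arm and all their MRI data used.

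The cost is a few sentences, with no change to sample size, visits or procedures. The dosing provisions of Protocol 9.1.6 are not touched; only the analysis of affected participants is specified. The downside is the loss shown in step 4 of the working: an affected participant contributes nothing to the primary model. Once item 2 is in place, item 1 therefore does not alter the primary contrast for that participant. It makes the grouping agree with the estimand and fixes the arm in the supportive analysis. For this reason item 4 should not be omitted.

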#### **4.1.4 Handling of missing values/censoring/discontinuations**

Some intermittently missing data may be expected due to participants occasionally missing a study visit while continuing with the randomized treatment. Such data will be implicitly imputed by the MMRM under the MAR assumption. Only participants with a baseline and at least one post-randomization measurement will be included in the primary analysis.

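### A participant moved to the other LRX712 dose after an arm is stopped still counts under the first dose, so mixed-dose MRIs enter the single-dose primary contrast

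*SAP*

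**What the plan says.** - **The switch is planned conduct.** Under Protocol 9.1.6, if a paused arm is stopped, a participant who has not had all three doses may go on once the investigator and sponsor agree it is safe; then "he/she will continue the study on the other dose level until completing the full dosing regimen". The unfilled places move too: "The pending number of subjects that would have been randomized to the stopped treatment arm will be randomized to the other treatment arm". The protocol's own example is "if the 25 mg LRX712 treatment arm was stopped after 5 subjects were randomized to it".
- **Grouping.** SAP 3.3: "For all analysis sets, participants will be analyzed according to the study treatment(s) initially received". Protocol 12.1 lacks the word initially: "For all analysis sets, subjects will be analyzed according to the study treatment(s) received".
- **Intercurrent events.** The list in SAP 1.4 has one entry: "At least one dose administration missed". SAP 4.1.3 discards data after the events listed in 1.4 and aims at the effect "if all participants adhered to the initially randomized treatment through that time point".
- **Exclusions.** SAP Table 3-1 removes participants only for missing consent. SAP 4.1.1 removes only the three 75 mg participants from the models.
- **Primary analysis.** SAP 4.1.1 compares 15 mg with placebo and 25 mg with placebo at Week 28, separately. SAP 4.1.4: "Only participants with a baseline and at least one post-randomization measurement will be included in the primary analysis".
- **Timing.** The last injection is at Week 8. Protocol 3.2 places the MRIs at Screening and Weeks 16, 28 and 52.
- **Other data.** SAP 6 summarises PK by treatment. SAP 5.1 summarises adverse events by treatment. SAP 5.4.1 assigns each ECG to the dose actually given.

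**The concern.** Grouping by first treatment would suit a treatment-policy estimand. This SAP chose a hypothetical one: the effect had everyone kept to the randomized dose. A switcher has not kept to it, yet no rule removes or marks that participant's scans. The stopped dose's volume estimate would then mix two regimens under one label and would not answer the question in SAP 1.4. The same label would cover PK concentrations and adverse events that arose on the other dose, while ECGs in the same report would follow the dose given.

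The rule takes effect only when an arm has been stopped for tolerability. That arm is then likely to be small, so a few switchers can dominate it.

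There is also a safety side. Protocol 9.1.6 describes switching and reallocation in both directions and mentions the lower dose only as an example. Read literally, stopping 15 mg for tolerability would send participants and remaining places up to 25 mg. The protocol's Amendment 4 rationale puts the estimated probability of local reactions at 5% above placebo for 15 mg and 10% above placebo for 25 mg.

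**Working it through.** **1. The plan's own figure.** Inputs (Protocol 12.8.1, SAP 7): difference 123 mm³, SD 130 mm³, 13 per arm, two-sided 10%. The noncentrality is 123 / (130 × √(1/13 + 1/13)) = 2.41. The normal approximation gives 77.9%, matching the SAP's 78%. The noncentral t with 24 df gives 75.8%, in line with the protocol's 75%. Neither is in dispute.

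**2. The path of a switcher who receives three injections.**
- Dose missed? No, so there is no listed intercurrent event.
- Protocol deviation? No, because the protocol prescribes the switch.
- Excluded by Table 3-1 or as a 75 mg participant? No.
- Group? The first dose received.
- Post-baseline MRIs after the last injection? Weeks 16, 28 and 52, so 3 of 3.

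**3. Dose received in a switch from 25 to 15 mg.** Planned totals are 3 × 25 = 75 mg and 3 × 15 = 45 mg, a separation of 30 mg.

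| Switch at | Total dose | Separation from the 15 mg arm kept |
|---|---|---|
| Injection 2 | 25 + 15 + 15 = 55 mg | (55 − 45)/30 = 33% |
| Injection 3 | 25 + 25 + 15 = 65 mg | (65 − 45)/30 = 67% |

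**4. PK samples (Protocol Table 8-2).** Day 1 (three), then Days 2, 8, 29 pre-dose, 30, 36, 57 pre-dose, 58, 64, 113 and 197: 13 in total. After a Day 29 switch, 7 follow the other dose. After a Day 57 switch, 4 do.

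**5. Share of the stopped arm.** Take the protocol's example of 5 randomized to 25 mg. Assume the two participants whose reactions triggered the stop discontinue before injection 3 and drop out of the model through the missed-dose event, leaving 5 − 2 = 3. If 1, 2 or 3 of these switch, the mixed-dose share at Week 28 is 1/3 = 33%, 2/3 = 67% or 3/3 = 100%. In an arm with 13 evaluable participants, one switcher is 1/13 = 8%.

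**6. Possible shift in mm³.** Let f be the mixed-dose effect as a fraction of the full 25 mg effect, s the number of switchers and n the number evaluable. The expected contrast is 123 × [1 − (s/n)(1 − f)]. The documents do not give f, so the values below are assumptions. With n = 3:

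| s | f = 0.5 | f = 0.75 | f = 1 |
|---|---|---|---|
| 1 | −20.5 | −10.3 | 0 |
| 2 | −41.0 | −20.5 | 0 |
| 3 | −61.5 | −30.8 | 0 |

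**7. What removing switchers costs.** Power against 13 placebo participants, noncentral t, same 123/130 assumption: 40.7% with 3 evaluable, 32.4% with 2 and 22.3% with 1.

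**8. Carry-over.** Protocol 1.3.2 reports a half-life of 239 h at 15 mg. After 28 days (672 h) the fraction left is 0.5^(672/239) = 0.14.

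**The case against.** The best reply is that this may never matter. An arm must be stopped, not merely paused, and a mid-course participant must then be cleared to go on. The SAP was amended in March 2025, still describes three arms and both contrasts, and mentions no stopped arm or switchers. That suggests no switch had occurred, without proving it. If none did, the gap changes no result.

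Other points also stand in part:
- In a switch from 25 to 15 mg, the continuing contrast of 15 mg with placebo receives no mixed-dose data. Only the stopped dose is affected.
- The sample size section assumes the same 123 mm³ for either dose, and Protocol 1.3.2 saw no clear relation between dose and synovial exposure. If both doses work equally (f = 1), the shift is nil. The milligram separation in step 3 describes the regimen and is not a bias in mm³.
- The 33% to 100% shares need the remaining participants to be mid-course. Those who have finished do not switch, and those not yet dosed would simply start on, and count as, 15 mg.
- The 14% carry-over uses the 15 mg half-life because none is stated for 25 mg. PK samples taken outside their window are left out of the summaries anyway.

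Two arguments do not close the gap. SAP 4.1.3 introduces the missed dose as an instance, which might be stretched to cover a switch, but the same paragraph refers back to the one-item list in SAP 1.4. A safety pause might also cause a dose to be missed, but the SAP does not say whether a delayed dose counts. Both would leave the decision until after the data are seen.

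**Conclusion.** The concern holds. Followed as written, the plan puts the scans of a switcher who completes three injections into a single-dose contrast, against its own stated target. These objections bear on how likely and how large the effect is; they do not change what the rules do.

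Per switcher, 3 of 3 post-baseline MRIs and 7 or 4 of 13 plasma samples are affected. The share of the arm runs from 8% (one switcher among 13 evaluable) to 33–100% in the stopped-after-5 example, under the stated assumption about the two reactors. Neither the probability of a switch nor the bias in mm³ can be estimated from the documents, and the bias could be zero. This should be corrected, but it threatens the trial's results only if an arm is actually stopped.

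**What to change.** 1. **SAP 1.4 and 4.1.3.** Add a switch to the other dose level as an intercurrent event under the same hypothetical strategy, and say whether a delayed injection counts as missed. Because every post-baseline MRI comes after dosing, switchers would have no usable post-baseline value and would leave the primary model under SAP 4.1.4. State this and show their results separately. The optional pooled LRX712 analysis in Protocol 12.4.4 can also take them.
2. **SAP 3.3, 5.1 and 6.** Summarise post-switch PK concentrations and parameters apart from the first dose group. Flag post-switch adverse events and other safety data, or show them by the dose actually given, with a note on carry-over.
3. **Protocol 9.1.6.** State that both switching and reallocation of places go only from 25 mg to 15 mg. The reallocation clause matters most, because the investigator and sponsor safety agreement covers participants already randomized and not the remaining places.

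**Cost.** SAP wording, a switch flag from dosing records already kept, and one protocol sentence. The real loss is the switchers' MRIs. In the stopped-after-5 example with 1 to 3 switchers, 2 to 0 evaluable 25 mg participants remain and that contrast becomes descriptive. Little is given up, since keeping all three would give only about 41% power.
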